7.4. Treatment Assessments

Study treatment will be given in 4-week (28-day) cycles (± 5 days) for all patients.

7.4.1. Day 1 of Each Cycle

The following assessments will be performed on Day 1 of each cycle:

- Medical history
- Physical examination including measurements of weight and vital signs (resting heart rate, blood pressure, respiratory rate, and oral temperature) (**weekly during Cycle 1 for Lead-in patients**)
- ECOG performance status
- AE assessment (**weekly during Cycle 1 for Lead-in patients**)
- Concomitant medication review (**weekly during Cycle 1 for Lead-in patients**)
- CBC, including 3-part differential and platelets (Day 1 of each cycle ± 3 days) (**weekly during Cycle 1 for Lead-in patients**)(need not be done on Cycle 1 Day 1 if baseline was taken within 72 hours of that day)

CONFIDENTIAL

STUDY DRUG: Orteronel

SCRI INNOVATIONS STUDY NUMBER: BRE 203

DATE OF PROTOCOL: Version 3.0 30 October 2013

- CMP (Day 1 of each cycle \pm 3 days) (**weekly during Cycle 1 for Lead-in patients**) (need not be done on Cycle 1 Day 1 if baseline was taken within 72 hours of that day)
- Serum hormone levels: estradiol, total and free testosterone, SHBG, ACTH, DHEA-S, and cortisol (**Day 1 of Cycles 2, 4 and End of Treatment only** [see Section 7.5])
- Serum amylase/lipase
- Serum/urine pregnancy test (for women of childbearing potential only). If the baseline reading was done within 72 hours of Cycle 1 Day 1, this test need not be repeated on that day.
- Study drug compliance assessment

7.4.2. Day 1 of Cycle 3 and Every Other Cycle Following (Cycles 5, 7, 9, etc), except where noted

- Fasting plasma glucose, insulin, c-peptide, and HbA_{1c} (only in patients with a history of diabetes)
- 12-lead ECG
- CT scan of the chest /abdomen/pelvis (only those scans abnormal at baseline need to be repeated)
- Bone scan (if clinically indicated)
- CT/MRI of the brain (if clinically indicated)

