5. STUDY DESIGN

This is an open-label, multicenter, Phase II study to be conducted in 2 stages. All patients will receive orteronel PO at a dose of 300 mg twice daily (BID) (600 mg total daily dose).

- Lead-in Phase: The first 6 patients treated will be evaluated every week to confirm the safety and feasibility of this regimen. After all 6 patients complete at least 4 weeks of treatment, and if no prohibitive toxicities are identified, continuous study treatment will begin.
- Continuous Study Treatment: Patients will continue to be enrolled into both cohorts based on their tumor specificities up to a total of 31 patients in Cohort 1 (ER-/PR-/HER2-/AR+) and 55 patients in Cohort 2 (ER+ and/or PR+/AR+). These numbers include the patients that are participating in the lead-in phase.

Up to 86 patients are planned to be enrolled in this study (6 for the lead-in phase and 80 for continuous study treatment).

Patients will be evaluated every eight weeks for response to treatment.

All patients who respond to treatment (complete response [CR] or partial response [PR]) or have stable disease (SD) will continue to receive orteronel until they develop progressive disease (PD) or unacceptable toxicity.

The study design schema is presented in Figure 1.

[figure not shown]
CONFIDENTIAL

STUDY DRUG: Orteronel

SCRI INNOVATIONS STUDY NUMBER: BRE 203

DATE OF PROTOCOL: Version 3.0 30 October 2013

Figure 1. BRE 203 Treatment Schema

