7.3. Full Screening

Consent for the main study must be obtained ≤ 28 days prior to the initiation of study treatment. The baseline assessments described in Appendix E will be collected prior to the initiation of treatment. Baseline ECHO/MUGA should be within 28 days of treatment.

The physical examination, ECOG performance status, serum/urine pregnancy test (for women of child-bearing potential only), and complete blood counts (CBCs) should be done ≤ 7 days prior to initiation of treatment. All other assessments should be performed ≤ 4 weeks prior to initiation of treatment.

- Signed informed consent prior to any other study-related procedures
- Medical history (including assessment of baseline signs and symptoms)

CONFIDENTIAL

STUDY DRUG: Orteronel

SCRI INNOVATIONS STUDY NUMBER: BRE 203

DATE OF PROTOCOL: Version 3.0 30 October 2013

- Physical examination including measurements of height, weight, and vital signs (resting heart rate, blood pressure, respiratory rate, and oral temperature)
- Eastern Cooperative Oncology Group Performance Status (ECOG) performance status (Appendix A)
- Concomitant medication review at the time of informed consent
- Complete blood count (CBC) including 3-part differential and platelets) (may be done up to 72 hours prior to treatment)
- Comprehensive metabolic profile (CMP) (Section 7.6.3) (may be done up to 72 hours prior to treatment)
- Fasting plasma glucose, insulin, c-peptide, and HbA_{1c} (only in patients with a history of diabetes)
- Serum amylase, lipase
- Serum hormone levels: estradiol, total and free testosterone, SHBG, ACTH, DHEA-S, and cortisol
- Serum/urine pregnancy test (for women of childbearing potential only). If done within 72 hours prior to treatment, this test need not be repeated on Cycle 1 Day 1.
- 12-lead ECG
- ECHO/MUGA
- Urinalysis
- CT scan of the chest/abdomen/pelvis
- Bone scan, if clinically indicated
- CT/MRI of the brain, if clinically indicated

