7.5. End of Study Treatment

Patients are permitted to continue treatment with orteronel until disease progression, or the patient is discontinued due to unacceptable toxicity or a decision to discontinue treatment by the patient or the study physician. Patients will return to the study center \leq 30 days after treatment ends for the following assessments:

- Update of medical history
- Physical examination including measurement of weight and vital signs
- ECOG performance status
- AE assessment
- Concomitant medication review
- Study drug compliance assessment
- CBC, including 3-part differential and platelets
- CMP
- Fasting plasma glucose, insulin, c-peptide, and HbA_{1c} (only in patients with a history of diabetes)
- Serum hormone levels: estradiol, total and free testosterone, SHBG, ACTH, DHEA-S, and cortisol

CONFIDENTIAL

STUDY DRUG: Orteronel

SCRI INNOVATIONS STUDY NUMBER: BRE 203

DATE OF PROTOCOL: Version 3.0 30 October 2013

- Serum amylase/lipase
- Urinalysis
- CT scan of the chest /abdomen/pelvis, if no documented progressive disease and the last assessment was >8 weeks prior (only those scans abnormal at baseline need to be repeated)

If treatment is discontinued because of toxicity or any other reason(s) at a treatment visit and no study treatment is administered, that visit may fulfill the End-of-Treatment Visit.

After withdrawal from protocol treatment, patients must be followed for AEs for 30 calendar days after the last dose of study drug.

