9.2.2. Response Criteria

Evaluation of Target Lesions

Complete Response (CR): Disappearance of all target lesions.

Partial Response (PR): At least a 30% decrease in the sum of the longest diameter (LD) of target lesions, taking as reference the baseline sum LD.

Stable Disease (SD): Neither sufficient shrinkage to qualify for PR nor sufficient increase to qualify for PD, taking as reference the smallest (nadir) sum LD since the treatment started.

Progressive Disease (PD): At least a 20% increase in the sum of the LD of target lesions, taking as reference the smallest (nadir) sum since the treatment started, or the appearance of one or more new lesions. Requires not only 20% increase, but absolute increase of a minimum of 5 mm over sum.

Evaluation of Non-Target Lesions

Complete Response (CR): Disappearance of all non-target lesions and normalization of tumor markers. All lymph nodes must be non-pathological in size (<10 mm short axis).

Stable Disease (SD): Persistence of one or more non-target lesions and/or persistence of tumor marker level above the normal limits.

Progressive Disease (PD): Appearance of one or more new lesions and/or unequivocal progression of existing non-target lesions. When the patient also has measurable disease, to achieve “unequivocal progression” on the basis of the non-target disease, there must be an overall level of substantial worsening in non-target disease such that, even in presence of SD or PR in the target disease, the overall tumor burden has increased sufficiently to merit discontinuation of therapy.

Evaluation of Best Overall Response

The best overall response is the best response recorded from the start of the treatment until disease progression/recurrence (taking as reference for progressive disease the smallest measurements recorded since the treatment started). In general, the patient's best response assignment will depend on the achievement of both measurement and confirmation criteria.

Confirmation of response (by repeat scans after 4 weeks or as specified in the protocol) is required for trials in which response rate is the primary endpoint, but is not required in randomized trials or trials with primary survival endpoints (i.e., where response is not a primary endpoint).

CONFIDENTIAL

STUDY DRUG: Orteronel

SCRI INNOVATIONS STUDY NUMBER: BRE 203

DATE OF PROTOCOL: Version 3.0 30 October 2013

Target Lesions	Non-Target Lesions	New Lesions	Overall Response
CR	CR	NO	CR
CR	SD	NO	PR
CR	NE	NO	PR

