Appendix E: Schedule of Assessments for BRE 203 (continued)

- ^a Physical examinations will include measurements of vital signs (resting heart rate, blood pressure, respiratory rate, oral temperature). At the baseline visit only, height will also be recorded and weight will be recorded only on Day 1 of each cycle.
- ^b Hematological parameters include the following laboratory tests: complete blood count consisting of red blood cell count (RBCs), hemoglobin, total white blood count (WBC) with differential, and platelet count. Do not repeat on C1D1, if baseline within 72 hours.
- ^c CMP assessment includes the following laboratory tests: glucose, BUN, creatinine, sodium, potassium, chloride, calcium, CO₂, alkaline phosphatase (ALP), AST, ALT, total bilirubin, total protein, and albumin. Do not repeat on C1D1, if baseline within 72 hours.
- ^d Fasting plasma glucose, insulin, and c-peptide will be drawn at screening, predose on Day 1 of odd-numbered cycles (Cycles 3, 5, 7, etc), and at study completion for patients with a history of diabetes.
- ^e A single ECG will be obtained at baseline for QTcF interval assessment for all patients. A single ECG will also be obtained predose on Cycle 3 Day 1 and then every 2nd cycle (Cycles 5, 7, 9, etc).
- ^f Archived tumor tissue from a primary biopsy or metastatic lesion is required for centralized testing of AR expression. Patients with AR expression $\geq 10\%$ will be screened for enrollment into the study. Additional tumor tissue, if available from the patients enrolled on study, will be retained to perform correlative testing (15 to 20, 4 um unstained slides). Patients may enroll based on local laboratory AR assessment, but will need to submit tissue for confirmation at the central laboratory.
- ^g Informed consent must be obtained ≤ 28 days prior to the initiation of trial treatment. The physical examination, ECOG performance status, serum/urine pregnancy test (for women of child-bearing potential only), and complete blood counts (CBCs) should be done ≤ 7 days prior to initiation of treatment.
- ^h If clinically indicated.
- ⁱ Day 1 of each cycle following Cycle 1
- ^j Serum hormone levels will be drawn at screening, on Day 1 of Cycles 2 and 4, and at the end of study visit.
- ^k Do not repeat on Cycle 1 Day 1, if baseline was done within 72 hours.
- ^l Lead-in patients only
- ^m If no documented progressive disease and the last assessment was >8 weeks prior. Only abnormal scans at baseline need to be repeated.

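### On-study CT need not cover regions that were normal at baseline, so new lesions there can be missed or found late, and DCR and PFS can be biased only upward

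*Combined protocol and SAP*

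**What the plan says.** Screening includes a "CT scan of the chest/abdomen/pelvis" (Section 7.3). On treatment, at Day 1 of Cycle 3 and every second cycle after that, Section 7.4.2 lists "CT scan of the chest /abdomen/pelvis (only those scans abnormal at baseline need to be repeated". At end of treatment, Section 7.5 asks for the CT "if no documented progressive disease and the last assessment was >8 weeks prior (only those scans abnormal at baseline need to be repeated". Footnote m of the Appendix E schedule combines the two conditions: "If no documented progressive disease and the last assessment was >8 weeks prior. Only abnormal scans at baseline need to be repeated". Bone imaging on study is listed as "Bone scan (if clinically indicated" (Section 7.4.2).

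Section 5 sets the assessment interval: "Patients will be evaluated every eight weeks for response to treatment". In Section 9.2.2, PD is a sufficient increase in the target lesions "or the appearance of one or more new lesions", and every row of the overall-response table that gives CR, PR or SD has NO under new lesions.

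Section 10.6.1 defines DCR, a primary endpoint in both cohorts, through absence of progression among patients evaluable at 6 months. Section 10.6.2 counts a PFS event at objective progression or death and otherwise censors at the last adequate tumour assessment. The term adequate is not defined.

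**The concern.** The response criteria need a statement about the whole body, namely that there are no new lesions. The imaging schedule requires information only about regions that already showed disease. A patient with disease confined to the lung could develop a silent abdominal metastasis, have stable lung lesions on the only CT the protocol requires, and be recorded as SD with no new lesions.

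The error runs in one direction. Leaving a region unscanned can conceal PD; it cannot produce a false PD. With no randomised control there is no second arm with the same error to set against it. What is at stake is the reported DCR, the PFS curve and, less often, an objective response credited after an unseen new lesion.

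Footnote m raises a separate, smaller problem. Its timing condition belongs to the end-of-treatment visit in Section 7.5, but the footnote appears to govern the on-treatment scans as well.

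**Working it through.** **Is there a planned figure to reproduce?** Not for imaging. The sample sizes rest on response alone, and the two-stage rules in Sections 10.3 and 10.4 reproduce by exact binomial calculation. Cohort 1 (stop at 0 of 19, success at 2 or more of 28) has alpha 0.0985 and power 0.801. Cohort 2 (stop at 1 or fewer of 26, success at 5 or more of 50) has alpha 0.0973 and power 0.806. Nothing below changes these figures.

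**DCR if the lesion stays undetected to 6 months.** Let D be the true 6-month DCR and q the share of true progressors whose only progression is a new lesion in a region not re-imaged. Neither is in the documents; both are assumed. Then

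reported DCR = D + (1 − D) × q.

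| D | q = 5% | q = 10% | q = 15% |
|---|---|---|---|
| 20% | 24.0% | 28.0% | 32.0% |
| 30% | 33.5% | 37.0% | 40.5% |
| 40% | 43.0% | 46.0% | 49.0% |

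For D = 30% and q = 10%: 0.30 + 0.70 × 0.10 = 0.37. In 50 evaluable patients that is 50 × 0.70 × 0.10 = 3.5 extra patients counted as controlled.

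**If detection is only delayed.** A simulation used exponential progression times (assumed true medians of 2, 3, 4 and 6 months), detection on an 8-week grid, q of 5%, 10% or 20%, and a delay of one or two visits: 4 × 3 × 2 = 24 scenarios.

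- The proportion without detected progression at week 24 rose by 0.6 points (14.7% to 15.3%) to 7.6 points (14.7% to 22.3%).
- Mean PFS rose by about 0.1 to 0.7 months.
- Median PFS was unchanged in 23 of the 24 scenarios, because it sits on the visit grid. It moved from 3.7 to 5.5 months in one (true median 3 months, q = 20%, two-visit delay).

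For a like-for-like comparison, take a true median of 3 months and q = 10%. The week-24 proportion is 27.9% with full detection, 29.4% with a one-visit delay, 31.7% with a two-visit delay, and 0.279 + 0.721 × 0.10 = 35.1% if the lesion is never found by then.

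**Footnote m, read literally on the on-treatment column.** Cycles are 28 days (Section 7.4), and baseline CT may be up to 4 weeks before treatment (Section 7.3). More than 8 weeks means more than 56 days.

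- Baseline to Cycle 3 Day 1: 56 days plus 1 to 28 days = 57 to 84 days. The condition is met and the scan is required.
- Cycle 3 to Cycle 5: 2 × 28 = 56 days. The condition is not met and an on-schedule scan is waived.
- Cycle 3 to Cycle 7, with Cycle 5 skipped: 112 days. The condition is met and the scan is required.

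The literal effect is a 16-week gap between Cycle 3 and Cycle 7, where Sections 5 and 7.4.2 call for 8 weeks.

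**The case against.** The restriction appears consistently in three places, so it looks deliberate, and it spares patients radiation. It is also a minimum: sites may scan more widely. History, physical examination, performance status and a metabolic profile that includes liver tests are due on Day 1 of every cycle and can prompt imaging. DCR has no success threshold, only an estimate with intervals, and the go/no-go rules use response alone. The size of the bias is assumed throughout.

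Most of this stands, and it limits the point. A reader might infer that new lesions outside the original regions will not be looked for at all. The text supports only that imaging them is not required. A reader might also infer that each missed lesion adds at least one 8-week interval to PFS. That does not follow, because visits are 4-weekly and clinical findings, target-lesion growth or death can end PFS sooner. Nor can one say by how much the Cohort 2 result would be flattered against the published 30% clinical benefit rate, since the documents do not describe how that study imaged its patients.

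On footnote m, a reader might infer that Appendix E cancels every on-treatment scan. The dates above show otherwise: Cycle 3 is always required when the baseline CT precedes Day 1, Cycle 7 is required if Cycle 5 was skipped, and the ±5-day window can bring Cycle 5 back in. The footnote's placement is also partly inferred. Only two CT marks follow screening and both carry m, which fits the Cycle 3/5/7 and End of Treatment columns. The superscripts may not be wholly reliable, though: footnote i seems to be attached to nothing, while the compliance row carries the lead-in letter. The placement should be confirmed in the typeset table.

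What the objection does not answer is the silent lesion. Examination and blood tests do not stand in for imaging when PD rests on a new lesion and the endpoint rests on PD.

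**Conclusion.** The point holds as a mismatch between the imaging schedule and the progression rule. Followed exactly, the plan permits a record of no new lesions for regions not imaged since baseline, and any resulting error in DCR and PFS is upward. Only the direction follows from the documents. The illustrative sizes are +3.5 to +10.5 points on a true DCR of 30% (q = 5% to 15%, undetected to 6 months), and less if detection is only delayed. For scale, the exact 95% interval for 15 of 50 is 17.9% to 44.6%; the shift is within that width, but a confidence interval makes no allowance for bias.

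A reader might infer that the stopping and success rules are compromised. They are not in general: they count responses, and a response is wrongly counted only where a hidden new lesion was already present when CR or PR was credited.

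The gap is widest for bone-only patients, who are eligible under Section 3.1. If their body CT is normal at baseline, no on-study imaging is mandatory.

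The footnote m conflict is real but minor: as worded, it waives an on-schedule Cycle 5 scan that Section 7.4.2 requires.

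**What to change.** 1. In Sections 7.4.2 and 7.5 and in footnote m, replace the baseline-abnormal limit with the same chest, abdomen and pelvis CT coverage as at baseline, at each scheduled tumour assessment. As a minimum, require full coverage at the assessment used for 6-month DCR and at any scan first showing CR or PR. The protocol should name the DCR visit; Cycle 7 Day 1 is 6 × 28 = 168 days, or week 24. The cost is amendment wording and some added CT regions with their radiation, for most patients in a session already scheduled. The minimum version is cheaper but leaves PFS uncorrected.

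2. Split footnote m so that the more-than-8-weeks condition applies only to End of Treatment, as in Section 7.5, and the Cycle 3/5/7 scans are unconditional, as in Section 7.4.2. This costs nothing.

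3. Define an adequate tumour assessment for PFS censoring in terms of the regions imaged. The CT change does not schedule bone imaging, so state separately how bone-only disease is to be followed.

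If data have already been collected, report how many assessments omitted a region and add a sensitivity analysis of DCR and PFS. Scans that were never taken cannot be recovered later, which is the reason to amend early.

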7.5. End of Study Treatment

Patients are permitted to continue treatment with orteronel until disease progression, or the patient is discontinued due to unacceptable toxicity or a decision to discontinue treatment by the patient or the study physician. Patients will return to the study center \leq 30 days after treatment ends for the following assessments:

- Update of medical history
- Physical examination including measurement of weight and vital signs
- ECOG performance status
- AE assessment
- Concomitant medication review
- Study drug compliance assessment
- CBC, including 3-part differential and platelets
- CMP
- Fasting plasma glucose, insulin, c-peptide, and HbA_{1c} (only in patients with a history of diabetes)
- Serum hormone levels: estradiol, total and free testosterone, SHBG, ACTH, DHEA-S, and cortisol

CONFIDENTIAL

STUDY DRUG: Orteronel

SCRI INNOVATIONS STUDY NUMBER: BRE 203

DATE OF PROTOCOL: Version 3.0 30 October 2013

- Serum amylase/lipase
- Urinalysis
- CT scan of the chest /abdomen/pelvis, if no documented progressive disease and the last assessment was >8 weeks prior (only those scans abnormal at baseline need to be repeated)

If treatment is discontinued because of toxicity or any other reason(s) at a treatment visit and no study treatment is administered, that visit may fulfill the End-of-Treatment Visit.

After withdrawal from protocol treatment, patients must be followed for AEs for 30 calendar days after the last dose of study drug.

7.6. Follow-Up

7.6.1. Follow-Up After Discontinuing Study Treatment

Patients discontinuing treatment for any reason other than progressive disease will be monitored for evidence of disease progression. Disease progression will be assessed every 6 months for 2 years and annually thereafter, up to a maximum of 5 years after the last patient has enrolled on the study. Imaging scans will be done as clinically indicated for evaluation of any new symptoms and assessment for disease progression. After disease progression is documented, patients will be followed as specified in Section 7.6.2.

7.6.2. Follow-Up After Disease Progression

After disease progression is documented, survival will be monitored every 6 months for 2 years and annually thereafter, up to a maximum of 5 years after the last patient has enrolled on the study. Patients may be contacted during outpatient visits or by telephone.

7.6.3. Comprehensive Metabolic Profile

The following laboratory tests should be performed for each patient for assessment of CMP:

- glucose
- blood urea nitrogen (BUN)
- creatinine
- sodium
- potassium
- chloride
- calcium
- carbon dioxide (CO₂)
- alkaline phosphatase (ALP)
- AST
- ALT
- total bilirubin
- total protein

CONFIDENTIAL

STUDY DRUG: Orteronel

SCRI INNOVATIONS STUDY NUMBER: BRE 203

DATE OF PROTOCOL: Version 3.0 30 October 2013

- albumin

